Main eligibility criteria	
Inclusion:
 
 • Patient and disease factors are deemed suitable for transoral surgery under general anaesthetic. • Decision to treat with primary transoral resection or local excision biopsy. • Aged 18 or over. • Written informed consent provided. • Clinically suspected or histologically confirmed primary dysplasia or malignancy of the oral cavity or oropharynx OR histologically confirmed diagnosis of squamous cell carcinoma in a cervical lymph node of unknown primary. • Patient considered fit for surgery. 
Exclusion:
 
 • Lesions undergoing incisional or punch biopsy only. • Surgery with planned primary closure or local/ distant flap reconstruction. • Inability to provide written informed consent. • Medical contraindication to a general anaesthetic or to PuraBond® use.
Interventions	
Two existing operative techniques:
 
 i) PuraBond® application to surgical field ii) No PuraBond® application to surgical field.
Follow up duration	1 month
Planned Study Period	TBD
Objectives	To test the hypothesis that in adult patients undergoing surgical excision procedures for mucosal pathology of the oral cavity or oropharyngeal subsites, the use of PuraBond® intraoperatively on the surgical bed significantly reduces acute pain at 30 days post randomisation. To compare the effectiveness of its use on the incidence of post-operative complications and important clinical outcomes.

3 Background, rationale and objectives

3.1 Background and rationale

Head and Neck Cancer (HNC) describes a host of different malignancies originating from various anatomical sites including the oral cavity, pharynx and larynx, with 90% of tumours being squamous cell carcinomas. In the UK, HNC is the eighth most common cancer type accounting for an estimated 12,422 new cases annually [1].

One particular subtype of HNC is oropharyngeal squamous cell carcinoma which relates to the structures of the oropharynx including the tonsils, base of tongue (BOT), soft palate and walls of the oropharynx. In 2018, the global incidence of oropharyngeal cancer (OPC) was just over 92,000 new cases [2]. Both premalignant oral lesions and OPC are treated with surgical excision and healing by secondary intention [3]. Surgery within this anatomical area means pain is an important side effect and as with all surgical procedures, intra-operative and post-operative bleeding is also a known consequence.

Developed by the company 3-D Matrix, PuraBond® (also known as PuraStat®; 3-D Matrix Ltd, Tokyo, Japan) is a novel haemostatic agent [4]. It utilises RADA16, a synthetic peptide normally viscous in consistency, that is organised in β -sheet nanofibers in acidic environments. However, upon exposure to biological fluids such as blood these sheets cross-link creating a stable interwoven transparent hydrogel 3-D matrix. This hydrogel acts as a barrier to prevent further blood flow from the operative wound site. Thus, its use controls local surgical haemorrhage and prevents post-operative re-bleeding. Its use as a haemostatic agent has been demonstrated in various surgical fields including endoscopic resection of gastrointestinal lesions, cardiac surgery and laparoscopic colorectal operations [5,6,7]. These studies confirmed PuraBond® as an effective operative haemostat. Packaged in a prefilled syringe, use of PuraBond® is thus practical within busy operating theatres. It was approved for use in the European Union (EU) in 2014 (with the United Kingdom a member state at this time) as a CE marked class III medical device. It is currently actively being used within routine head and neck cancer operations in Liverpool University Hospital Foundation Trust (LUHFT), although current use is variable and largely depends on surgeon preference.

Transoral approaches in head and neck surgery have become more common given they offer a minimally invasive approach to surgery, thus removing the need for external incisions in the neck. This surgical approach can involve using either a carbon dioxide laser or a robotic approach. A recent UK case series from Birmingham reported on the use of PuraBond® in thirteen oropharyngeal cancer cases treated with Transoral Robotic Surgery (TORS) [8]. No cases of primary or secondary haemorrhage post-operatively were recorded and all patients resumed oral diet on day one post operatively. The authors also alluded to better patient outcomes including swallowing, pain and length of stay in hospital. Although, the use of PuraBond® as a haemostatic agent is well documented, its impact on pain management is a clinically important factor of interest as pain directly impacts patient recovery. Yet this factor has not been studied within the parameters of a randomised control trial. The formation of the hydrogel barrier insulates the wound bed thus it may also reduce pain stimulus to the operative site. A clinical trial such as PuraBond® PROOF is needed to provide gold-standard evidence to support such findings and impact clinical management. This will provide real world evidence of PuraBond® use on pain outcomes in head and neck surgery.

3.2 Study objectives

The aim of this study is to assess whether intraoperative use of the haemostatic agent PuraBond® is associated with decreased levels of pain postoperatively following wide local excision procedures for oral or oropharyngeal mucosal lesions. We hypothesise that patients treated with such agents will have better post-operative pain scores compared to those treated without.

4 Study design

PuraBond® PROOF is a prospective, single centre, parallel group randomised controlled trial (RCT). Patients eligible for the study must have clinically suspected or histologically confirmed dysplasia or malignancy in the oral cavity or oropharyngeal subsites. Their primary lesion must be considered resectable via a transoral approach. After informed consent, patients will undergo baseline assessment of pain levels prior to surgery and demographic data will be collected. Surgery may or may not involve laser use to the primary site.

Suitable patients will be stratified prior to randomisation by lesion site (oral cavity or oropharynx) and whether or not the surgical technique will involve laser resection. Depending on which arm the participant is allocated to, PuraBond® may or may not be applied to the surgical bed intraoperatively. It is important to note that both treatments are routinely used in these operations and PuraBond® use will fall completely within its license in this study.

Using surgical site and technique to clinically stratify patients is important as standard post operative analgesia management differs between these groups (see table below). It is important that data collected from this trial represents real world evidence and thus, pre and post operative analgesia agents used will be recorded by analysing patient's prescriptions rather than. restricting analgesia prescriptions and changing current standard of care. This means this trial will not lack generalisability and will not limit the relevance of its results to real world practice.

Medication	Oropharyngeal surgery		Oral cavity surgery
	TOLR	No laser used	
Paracetamol	✓	✓	✓
Ibuprofen	✓	✓	✓
Codeine	✓	✓	✓
Morphine	✓	Not routinely used	Not routinely used
Oxycodone	X	Not routinely used	Not routinely used
Chlorhexidine	X	X	✓
Gelclair®*	✓	X	✓
Benzydamine 0.15% solution	✓	✓	✓
Pregabalin	✓	X	X

*Please note: Patients enrolled in PuraBond® PROOF will not be prescribed Gelclair® post operatively. Gelclair® is a viscous gel used orally that may confound any results of PuraBond use. It is a product licensed for treatment of oral mucositis in in oncology, hence use in our patient cohort is considered off label.

4.1 Study setting

This will be a single centre study undertaken at Liverpool University Hospitals NHS Foundation Trust (LUHFT) in Liverpool Head and Neck Centre. LHNC is the largest UK NHS/ University head and neck collaboration delivering research-driven high-quality patient care. It has developed a

large clinical trial portfolio with multiple international and national clinical trials supported at the centre. Thus, it provides an ideal clinical setting to ensure adequate patient recruitment into the study due to the large number of surgical head and neck operations conducted daily as well as research expertise.

Suitable patients will be identified by screening both daily operative lists at the centre as well as head and neck outpatient clinic lists and MDT. Suitable patients will then be approached by a member of the research team to confirm eligibility as well as discuss and provide information on the study and potential participation. All trial procedures including identification, recruitment, surgery and follow up will be undertaken within LUHFT.

5 Trial entry

5.1 Identification of participants

Patients will be identified directly from clinical lists of patients undergoing a predetermined list of surgical procedures involving either the oral cavity or oropharyngeal sites (see section 6). Patients will be identified by members of their normal clinical team or study team. Patients who appear to fulfil the inclusion criteria will be referred to the research team for confirmation. Eligibility will be formally confirmed by the CI, site PI, study co-investigators or delegates, who have access to, and a full understanding of, the patient's medical history. Once eligibility is confirmed the patient will be approached by a suitably delegated member of the trial team who will inform them of the trial. This may occur in a variety of settings e.g., in surgical clinics, pre-operative clinics and on pre-operative wards.

5.2 Screening procedures

Patients are eligible for the trial if they are undergoing surgical excision of either suspected or confirmed dysplasia or malignancy of an oral or oropharyngeal subsite, all inclusion criteria are met (see section 5.3) and none of the exclusion criteria apply (see section 5.4). The patient's written informed consent must be obtained before registration and any trial related procedures are undertaken (see section 12).

5.3 Inclusion criteria

Patients are eligible for the trial if **all** of the following criteria are met:

- Patient and disease factors are deemed suitable for transoral surgery under general anaesthetic.
- Decision to treat with primary transoral resection or local excision biopsy.
- Aged 18 or over.
- Written informed consent provided.
- Clinically suspected or histologically confirmed primary dysplasia or malignancy of the oral cavity or oropharynx OR histologically confirmed diagnosis of squamous cell carcinoma in a cervical lymph node of unknown primary.
- Patient considered fit for surgery.

5.4 Exclusion criteria

Patients are not eligible for the trial if **any** of the following criteria apply:

- Lesions undergoing incisional or punch biopsy only.
- Surgery with planned primary closure or local/ distant flap reconstruction.
- Inability to provide written informed consent.

- Medical contraindication to a general anaesthetic or to PuraBond® use.

6 Surgery

Surgery should only be carried out through the transoral route. Depending on the lesion subsite, suitable procedures include:

Oral cavity

Excision of a lesion from free oral mucosal surfaces with planned healing by secondary intention.

Oropharynx:

- Tonsillectomy
- Tongue base mucosectomy
- Lateral oropharyngectomy
- Tongue base resection
- Soft palate excision

It is important to note that all surgical procedures undertaken will be standard of care and agreed on before and regardless of trial participation. PuraBond® is already in use in head and neck surgery at LUHFT depending on the operating surgeon's preference and is currently on the recognised supplier list for the trust.

7 Registration and randomisation

Following clinical assessment, participants will be randomised to one of two trial arms using the method of minimisation. Randomisation will be performed centrally by the LCTC. Patient eligibility must be established prior to randomisation (see section 5.1) and patients must confirm their consent by providing a signed informed consent form (see section 12.1). Details of the trial enrolment will be recorded in the participant's electronic patient record. This will include confirmation of eligibility and the date of enrolment into the trial.

At registration the participant will be given a unique participant trial number. At randomisation the participant will be allocated to a treatment arm. To register or randomise a patient the relevant registration or randomisation case report form (CRF) should be completed and the LCTC contacted. Participants will be randomised centrally by a computer in a 1:1 ratio to either have PuraBond® applied to the surgical field or not intraoperatively. A minimisation algorithm will be used within the online randomisation system to ensure balance in the treatment allocation over the three following clinical variables:

- Surgical subsite: oral cavity or oropharynx
- Surgical operation: concurrent neck procedure (yes or no)
- Surgical technique: laser use (yes or no)

The operating surgeon will be informed by LCTC regarding the patient's treatment arm allocation. Due to the packaging of PuraBond® within pre-filled and labelled syringes, attempts to completely blind clinicians intraoperatively are not feasible. However, the patient, the assessors of postoperative outcomes and the study co-investigators will be blinded.

8 Trial endpoint assessments

The aim of the PuraBond® PROOF trial is to determine whether PuraBond® application intraoperatively on the surgical field significantly reduces postoperative pain in head and neck transoral operations. Assessment of secondary clinical outcomes such as hospital stay and time till oral intake alongside post operative complications are also important points to record consequently. The study will also briefly consider any health economic benefits of PuraBond® use.

Details of the assessments required are included in the CRF and are outlined below in the schedule of trial assessments (see section 8.4). With regards to the timing of assessments, the date of transoral surgery and thus whether PuraBond® is applied or not is classified as day 0.

8.1 Baseline (pre-operative assessments)

Pre-operative clinical investigation and preparation will be as per trust guidelines. Upon obtaining informed patient consent for participation in the study, the following data will be recorded:

- Informed Consent (written)
- Compliance to inclusion/exclusion criteria
- Assignment of unique patient ID
- Sex and age in years (on the day of surgery)
- Height in centimetres
- Weight in kilograms
- Diagnosis and indication for surgery
- Surgical plan

8.2 Intra-operative assessments

On the day of the operation (day 0), the following data will be recorded:

- Baseline VAS pain score
- Surgical plan
- WHO performance score
- Surgeon's survey

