8.4 Schedule of trial assessments

Assessment/ Procedure	Screening and baseline	Surgery (Day 0)	Day of discharge	Follow up					
				POD 1	POD 2	POD 4	POD 7	POD 14	POD 30
Eligibility (inclusion/ exclusion criteria)	x								
Written informed consent	x								
Registration	x								
Assignment of a unique participant identification number	x								
WHO performance score	x	x							
Randomisation		x							
Pain VAS score		x	x	x	x	x	x	x	x
Participant demographics – age, gender etc.	x								
Diagnosis and proposed surgery	x	x							
TOLR/ transoral surgical excision		x							
Surgeon's survey		x							
Return to theatre within 24 hours				x					
Length of hospital stay			x						
Readmission to hospital within 30 days									x
Return to theatre within 30 days									x
Intra operative complications			x						
Post operative complications				x	x	x	x	x	x
Time till oral intake			x	x					x

9 Adverse effects and safety reporting

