12.2 Outcome measures

12.2.1 Primary outcome measures

The primary outcome of this study will be pain following procedure. This will be measured using the visual analogue scale (VAS) which is a validated pain rating scale first used by Hayes and Patterson in 1921 [9]. Self-reported pain severity is recorded by marking a point on a 10cm line that represents a continuum between 'no pain' at one end and 'worst pain' at the other. VAS pain scores preoperatively and on days 1, 2, 4, 7, 14 and 30 postoperatively will be recorded.

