12.4 Statistical analysis

All data will be collected using the trial CRF and will be included in the final analysis. A detailed statistical analysis plan will be developed before the analyses are conducted. The following statistical considerations will be used in this study:

Data Summaries:

Continuous data are summarised as median (inter-quartile ranges) and categorical data are summarised as frequencies of counts (percentages). All VAS pain scores will be recorded to 1 decimal point.

Missing Data:

Missing data are assumed to be rare given the study methodology and short follow up period, and analyses are thus planned on a complete case basis.

Levels of Significance:

Statistical significance will be determined using the $p < 0.05$ significance level with all results presented alongside two-sided 95% confidence intervals.

Patient groups for analysis:

All analysis will be carried out on an intention to treat basis, retaining patients irrespective of any protocol violations.

Analysis of the primary outcome:

Analysis of the primary outcome will be carried out using Analysis of Covariance (ANCOVA) techniques. Here the post-operative pain score will be analysed as the primary outcome with the pre-surgical pain score being included as an adjusting covariate. Results will be presented in terms of the difference in means (95% confidence) intervals between the two groups.

13 Informed consent, ethical and regulatory considerations

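### The baseline VAS is not tied to a point before randomisation, and the complete-case ANCOVA drops any randomised patient who lacks it

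*Combined protocol and SAP*

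**What the plan says.** **Intention.** Section 4 says that, after consent, "patients will undergo baseline assessment of pain levels prior to surgery". Section 12.2.1 says "VAS pain scores preoperatively and on days 1, 2, 4, 7, 14 and 30 postoperatively will be recorded". Section 12.4 specifies an ANCOVA of the post-operative score "with the pre-surgical pain score being included as an adjusting covariate".

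**Operational instructions.** Section 8.1, the list of pre-operative baseline data, contains no pain score. Section 8.2, headed Intra-operative assessments, opens with "On the day of the operation (day 0), the following data will be recorded" and includes "Baseline VAS pain score". In the schedule (8.4), the row "Pain VAS score" is blank under screening and baseline. Its first mark is in the Surgery (Day 0) column, where randomisation and the operation are also marked.

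**Conditions for randomisation.** Section 7 says "Patient eligibility must be established prior to randomisation" and also requires a signed consent form. It does not name the baseline VAS. On blinding, the same section says "However, the patient, the assessors of postoperative outcomes and the study co-investigators will be blinded".

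**Missing data.** Section 12.4 expects missing data to be rare and plans complete-case analyses. It also says that all analyses follow intention to treat and keep patients whatever protocol violations occur. It gives no rule for a missing baseline score.

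**The concern.** The covariate in the primary model is needed from every patient, and it can be obtained only in a short window. The sections that staff work from leave that window undefined. The 8.2 list covers items from both sides of the intervention: the surgical plan and performance score belong before surgery, while the surgeon's survey, which section 12.2.2 says concerns ease of PuraBond use, can be completed only afterwards. Nothing in the list or the schedule says that the VAS comes before allocation, and nothing stops an allocation from being issued without it.

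Once the operation has taken place, a missed pre-surgical score cannot be obtained. Complete-case ANCOVA then excludes that patient even if all six post-operative scores were returned. This is an exclusion after randomisation, caused by a process failure, in a trial that says it retains everyone randomised.

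The plan also relies on this covariate for its size: the sample size was reduced on the strength of the baseline adjustment.

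**Working it through.** **Inputs from section 12.3:** SD 2.0; difference 1.2; multipliers 1.96 and 0.84; design factor (1 − 0.3) = 0.7 for baseline adjustment; 5% attrition; 32 per arm.

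**Step 1. Reproduce the plan's figure.**
- Unadjusted: n = 2 × (1.96 + 0.84)² × 2² / 1.2² = 62.72 / 1.44 = 43.56 per arm, or 87 in total. (The printed denominator is 1.96, but the printed result matches 1.44.)
- With factor and attrition: 87 × 0.7 × 1.05 = 63.9, so 64. The stated figure reproduces.
- The baseline adjustment is credited with saving 87 × 0.3 = 26.1 patients before attrition.

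**Step 2. Power if the only loss is the planned 5%.**
- Analysed: 64 × 0.95 = 60.8, or 30.4 per arm.
- Adjusted SD: 2 × √0.7 = 1.673.
- Power = Φ(1.2 / (1.673 × √(2/30.4)) − 1.96) = Φ(2.796 − 1.96) = 79.8%.

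The planned attrition therefore uses up the whole margin above 80%.

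**Step 3. Add missing baselines.** The rates are assumptions, because the documents give none. Per-arm n is 30.4 × (1 − rate), with the same formula.

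| Baseline missing | Analysed in total | Power |
|---|---|---|
| 0% | 60.8 | 79.8% |
| 5% | 57.8 | 77.8% |
| 10% | 54.7 | 75.6% |
| 20% | 48.6 | 70.6% |

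**Step 4. Does the loss depend on the design factor?** The usual ANCOVA factor for a correlation of 0.3 is 1 − 0.3² = 0.91. With it, power is 68.9% with none missing and 64.3% with 10% missing. The lower starting level is a separate sample-size question. The loss at 10% missing is similar: 4.6 points, against 79.8 − 75.6 = 4.2 points under the plan's factor.

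**Step 5. What mean imputation recovers.** Patients with an imputed baseline stay in the analysis but gain no variance reduction. As an approximation, the factor becomes (1 − m) × 0.7 + m × 1, with 30.4 per arm.
- m = 5%: factor 0.715, power Φ(2.766 − 1.96) = 79.0%, against 77.8% for complete cases.
- m = 10%: factor 0.73, power Φ(2.738 − 1.96) = 78.2%, against 75.6%.

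Imputation recovers more than half of the loss and keeps the analysed set in line with intention to treat. Collecting the score in the first place avoids the rest.

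**The case against.** The strongest reply is that the plan's intention is clear. Sections 4, 12.2.1, 12.3 and 12.4 all describe a pre-surgical score, and section 8 defines day 0 as the date of surgery, so a score taken that morning belongs in the day-0 column. On this view the 8.2 heading is only a loose label for day-0 data. Section 4 mentions baseline pain before stratification and randomisation, and section 7 says that randomisation follows clinical assessment. The score is collected while the patient is in hospital, so few should be missed. The CRF, which section 8 says holds the assessment details, is not available here, and section 12.4 promises a detailed analysis plan that could cover missing baselines.

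Much of this stands. A reader might infer from 8.2 that the score could be taken after waking, so that adjusting for it would remove part of a PuraBond effect. The documents do not support that: such a score would breach four sections of the protocol. Nor do they support a claim of material bias from a score taken after allocation but before surgery. The patient reports the score and is blinded, and PuraBond is applied only during the operation.

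Two things remain. The order of narration in section 4 is not a requirement, and section 7's explicit conditions leave the score out. The promise of a later plan does not alter the complete-case rule that section 12.4 already states.

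**Conclusion.** The point holds as a gap in procedure and in missing-data handling, not as a claim of bias. The protocol requires a pre-surgical score but does not place it before allocation or make randomisation depend on it. Its stated analysis would then discard randomised patients with outcome data, which conflicts with its intention-to-treat statement.

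The effect on power is modest: about 2 points if 5% of baselines are missing and about 4 points if 10% are, from a starting level of 79.8%. These figures rest on the plan's own SD, difference, design factor and attrition, and on assumed missing rates. If no baseline is missed, there is no loss. The change is still worth making, because it costs almost nothing and the score cannot be recovered after surgery.

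**What to change.** 1. List the baseline VAS in section 8.1 as a pre-operative item, taken before randomisation, and remove it from the intra-operative list in 8.2. Show the same timing in 8.4. A score on day 0 before allocation is acceptable; moving it to the screening visit is optional.
2. Make it a required field on the randomisation CRF that section 7 already uses, so that LCTC releases no allocation without it.
3. In section 12.4, replace complete-case handling of a missing baseline: any baseline VAS still missing takes the mean of all observed baseline scores, both arms pooled, so that every randomised patient with an outcome is analysed.

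The cost is one form check and one line of analysis. No visit is added, and the sample size stays at 64.
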